We propose the implementation and testing of a novel, highly efficient pragmatic intervention that seeks to shift the clinical practice paradigm of emergency medicine. We propose a pragmatic, cluster-randomized stepped wedge design to test the effectiveness of primary palliative care education, training, and technical support for emergency medicine (PRIM-ER) in 35 Emergency Departments (EDs). PRIM-ER includes four core components: 1) evidence-based multidisciplinary primary palliative care education, 2) simulation-based workshops on communication in serious illness, 3) clinical decision support, and 4) provider audit and feedback. These core components will be implemented in each participating health system as part of a quality improvement initiative to improve the care older adults with serious illness receive in the ED setting. In the UG3 phase of the project, we will: 1) tailor PRIM-ER to the emergency provider workforce and a more diverse ED context using an agile implementation framework approach; and 2) pilot test PRIM-ER at two sites for feasibility, fidelity, and usability. In the UH3 phase, we will: 3) implement PRIM-ER in a cluster-randomized, stepped wedge design in the remaining 33 EDs; and 4) measure the effect of PRIM-ER on aspects of: a) ED disposition to an acute setting; b) healthcare utilization in the 6 months following the ED visit; and c) survival following the index ED visit. The project will thus be implemented in a total of 35 EDs (2 pilot sites and 33 remaining EDs) as previously approved and outlined in the below table. We hypothesize that it will be feasible to test PRIM-ER at two EDs with a high level of fidelity and usability and implement at all sites. We also hypothesize that older adult visitors with serious, life-limiting illness cared for by providers with primary palliative care skills will be less likely to be admitted to an inpatient setting, more likely to be discharged home or to a palliative care service, and will have higher home health and hospice use, fewer inpatient days and ICU admissions at 6 months, and longer survival than those seen prior to implementation. Additionally, we hypothesize that sites with higher baseline ED disposition to an acute care setting and less primary palliative care knowledge and skills will demonstrate greater change after implementation.

Embedded under the PRIM-ER study, will be expanding our analysis to consider factors related to home and community services available for older adults with serious life-limiting illness, by considering contextual (regional, state, and healthcare-system) factors that influence access to home and community health services for older adults with serious life-limiting illness among the 18 PRIM-ER healthcare systems across the United

States. To understand the contextual factors we will conduct 1) an environmental scan/grey grey literature review to identify contextual factors impacting access to home and community health services, and 2.) Semi-Structured qualitative interviews with emergency medicine practitioners to capture provider perspectives and expand our contextual factors to include available resources in the healthcare service area. Throughout the protocol, we will continue to refer to these items as the PRIM-ER Contextual Assessment.

2. Background

The high intensity of end-of-life care in the United States (US) is now considered an epic public health problem. Persons receiving many life-sustaining therapies do not appear to show a benefit of better health or longer life.¹ Emergency Departments (EDs) care for society's most vulnerable older adults who present with exacerbations of chronic disease at the end of life, yet the clinical paradigm continues to focus on treatment of acute illness and injury. Palliative care interventions in the ED capture high-risk patients at a time of crisis and can dramatically improve patient-centered outcomes.^{2,3}

Half of Americans 65 years and older are seen in the ED in the last month of life, and three-quarters visit the ED in the six months before their death.⁴ Emergency care has not fully adapted to the needs or goals of seriously ill patients who prefer to have care delivered at home.^{5,6} Palliative care teams are now present in over two-thirds of hospitals, as well as 98 percent of National Cancer Institute-designated cancer centers.⁷ Consultation by palliative care teams, however, is typically available Monday through Friday during business hours, and palliative care teams are not routinely available to come to the ED when a patient is in crisis.

An ED visit is often described as a sentinel event signifying a breakdown in care coordination for older adults.^{8,9} Since EDs sit at the crossroads of ambulatory and inpatient care, they can and often play a pivotal role in balancing the potential harms and benefits of hospitalization for seriously ill, vulnerable older adults.¹⁰⁻¹³ Hospitalization for older adults carries significant risks such as iatrogenic complications, functional and cognitive decline, and loss of independence¹⁴⁻¹⁹ but emergency providers may be unaware of safe alternatives.

Emergency medicine developed as a specialty to treat the acutely ill and injured, yet EDs increasingly care for older adults with multiple comorbid conditions who present for acute exacerbations of chronic illness. Visits to the ED by older adults are increasing both in frequency and as a proportion of all ED visits. In 2011, adults aged 65 years and older comprised 15% of total ED visits, had the highest severity of illness, and represented 44% of all admissions from the ED.²⁰ The number and rate of admissions to the Intensive Care Unit (ICU) by emergency providers have also increased, especially among older adults.²¹ The proportion of the US population 65 years and older will continue to grow, and EDs will see an increase in both the number of older adults and the complexity of care they are required to provide.²² The ED presents a key decision point at which providers set the subsequent care trajectory, including whether an older adult is hospitalized and to which setting. Emergency physicians can thus play an integral role in transforming care for older adults through evidence-based models of care delivery that emphasize tradeoffs between potential benefits and potential harms.²³ However, until recently, little attention has been paid to the delivery of goal-concordant care in the ED for older adults with serious illness. The default treatment plan is to deliver treatment intensive care that favor life-sustaining therapies, many of which may be contrary to what older adults desire.

3. Settings of the Human Research

The PRIM-ER quality improvement (QI) initiative will be implemented in the Emergency Departments at the following sites:

Site	Location
NYU School of Medicine	
Perelman Center for Emergency Care	New York, NY
Bellevue Hospital Center	New York, NY
NYU Langone Hospital – Brooklyn	Brooklyn, NY
NYU Long Island	Mineola, NY
Allegheny Health Network	
Allegheny General Hospital	Pittsburgh PA

This is a cluster-randomized QI initiative that will implement and test the impact of PRIM-ER in various healthcare settings. We will first develop and pilot test the QI initiative at two sites in the UG3 phase, and then use a cluster-randomized, stepped wedge design to implement the education, training, and technical support in our network of EDs in the UH3 phase. Randomization will occur at the ED level and be done in advance by the biostatistician to determine the order in which the training will occur. Due to the COVID-19 pandemic, training will occur either in-person or virtually. The virtual trainings will occur using NYULH's Zoom account, meeting ID and set password. A member of the PRIM-ER team will be on each virtual training in order to monitor learner's attendance and assist with any technical glitches. The PRIM-ER team will provide the training link, meeting ID, and password to each Site Principal Investigator (PI) and the Site PI will distribute the link and meeting ID accordingly to his/her staff at their own home institution. Reminder e-mails about the training will be sent from each Site PI to his/her staff. The overall approach involves ongoing asynchronous learning and technical support to bolster skills, conduct interdisciplinary case reviews, and reinforce clinical pathways and protocols via provider audit and feedback. Electronic triggers for palliative care will be embedded in the electronic health record (EHR) to identify patients who may benefit from hospice or palliative care services. These electronic triggers already existing in the Perelman Center for Emergency Services EHR as part of standard, clinical workflow, but will be further tailored for each participating health system. Palliative care champions at each site will facilitate attendance at didactic and workshop sessions, disseminate information about local resources for outpatient palliative care, home care and hospice, and work with the local informatics team to reinforce protocols and implement trigger criteria to identify older adults who may benefit from further needs assessment and follow-up. We will engage with the palliative care champions to better understand the QI implementation process including but not limited to obtaining champion's feedback on the initiative, suggestions for improvements, and adaptations- all which are common approaches in implementing and reflecting on QI initiatives. Engagement will be in the form of discussions post QI about what went well, and what can be improved upon in moving forward as well as understanding from the champion's perspective what they could have done differently so the project team can gather lessons learned. Physicians and nurses will receive audit and feedback reports to monitor their performance over time, and a learning monitoring system will track participation in educational activities.

Prior to initiating this QI project, members from the palliative care team, emergency nursing, social work/case management, informatics, and ED operations from each of the 18 health systems will participate in workgroups to discuss how to best incorporate primary palliative care into the clinical workflow at each site. Pilot testing of PRIM-ER will also occur at two sites to optimize feasibility, fidelity, and usability. Emergency physicians at each pilot site will be invited to participate in usability testing of the clinical decision support (CDS) system. To assess usability, MORAE software will be utilized to perform screen captures and audio record participants verbalizing their actions, thoughts, and feelings as they progress through a simulated CDS system.

In the UH3 phase of the study, we will engage eligible providers at the 33 additional sites based on the random sequential order in which the ED implementation occurs. Throughout the duration of the project, we will actively

engage each health system by providing all ED staff with audit and feedback reports to monitor their performance over time. These reports will be provided on a weekly basis during the study period, as well as incorporated into ED-specific continuous quality improvement processes. By providing this continuous and consistent feedback to ED personnel, we hope to encourage continued participation and active engagement with the initiative throughout its duration. To understand the implementation barriers and facilitators for the CDS component, we will be asking each Site PI to complete a short REDCap quantitative survey describing the changes they made to their CDS component of the intervention and the rationale (instrument attached). Any PHI related to the person completing the quantitative survey will be completely optional (Title, Role, Age, Years in practice). We will require the Site name in order to understand the changes made at each site. We will be sending each survey to the Site PI, but if they are not equipped to complete the survey in entirely they can forward it to another team member (e.g. Information Technology analyst) within their institution. We only are interested in understanding the changes made at the site, nothing related to the person completing the survey on the site's behalf. We will also be conducting 30-60 minute qualitative interviews with Site PIs who are interested in an effort to gain more in-depth insights. Both the REDCap quantitative and qualitative interviews are completely optional. Verbal consent will be requested for qualitative interviews.

For the research component of the study, we will use Medicare claims of the beneficiaries in our patient cohort to measure outcomes, including ED disposition to an acute care setting, healthcare in the 6 months following the ED visit and survival following the index ED visit as a result of the intervention. The patient cohort will be extracted via the Centers for Medicare and Medicaid Services (CMS) Research Data Assistance Center (ResDAC) using a two-step process to maximize diversity, and minimize intentional or unintentional exclusions based on risk, age, health literacy, demographics, or expected adherence. First, we will provide a comprehensive list of facility codes for the 35 participating EDs. Inpatient and ambulatory claims will be used to identify community-dwelling ED visitors 66 years and over who made a visit to any of the EDs from 2 years prior to study initiation until the last day implementation day of PRIM-ER. ED claims will be identified via Revenue Center Code values of 0450-0459 (Emergency room) or 0981 (Professional fees-Emergency room) according to ResDAC. We will then examine all inpatient, ambulatory, and carrier claims for the 12 months prior to each older adult's index ED visit to calculate each beneficiary's Gagne Index, a score developed to predict one-year mortality in community-dwelling older adults.²⁴ The Gagne Index has been adapted from the Romano-Charlson Index and the Elixhauser system.^{25,26} It calculates a score based on the presence or absence of ICD-9s from inpatient and ambulatory claims in the prior year. Beneficiaries with a one-year mortality of at least 30% (score > 6) based on claims from the previous 12 months will be included in the analysis.

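### The protocol does not tie the start of audit and feedback, a core component, to each ED's crossover, and read literally its wording would send reports to EDs still in their control period

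*Combined protocol and SAP*

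**What the plan says.** The opening overview, before section 2 (Background), defines the package: "PRIM-ER includes four core components: 1) evidence-based multidisciplinary primary palliative care education", then communication workshops, then "3) clinical decision support, and 4) provider audit and feedback". It says the UH3 phase will "implement PRIM-ER in a cluster-randomized, stepped wedge design in the remaining 33 EDs".

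The procedures text after the site list in section 3 describes the roll-out a little differently. It will "use a cluster-randomized, stepped wedge design to implement the education, training, and technical support in our network of EDs", and "Randomization will occur at the ED level and be done in advance by the biostatistician to determine the order in which the training will occur". Audit and feedback appears later in that paragraph as a way of reinforcing pathways and protocols, with no start date.

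The UH3 paragraph first says that providers at the 33 sites are engaged in the random order of implementation. The next sentence opens "Throughout the duration of the project, we will actively" and continues "engage each health system by providing all ED staff with audit and feedback reports to monitor their performance over time". It is followed by "These reports will be provided on a weekly basis during the study period".

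The paragraph on baseline rates counts each site's time as baseline up to the month before that site's implementation.

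**The concern.** In a stepped wedge, an ED's time before crossover is the comparator for the other EDs and for its own later time. A core component that may reach an ED before crossover makes that comparator uncertain. The reports go to the clinicians whose disposition decisions form the primary outcome, so early reports could plausibly move it before the switch date.

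Any such exposure would most likely pull the estimate toward no effect, on the primary outcome and on the secondary outcomes that follow from it. Unless it is known when each ED first received reports, a null result could not be separated from a partly treated control period.

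**Working it through.** **Setting the texts side by side**

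| Place | What it fixes | Unit | Timing |
|---|---|---|---|
| Overview | All four components, including audit and feedback | ED | Stepped wedge |
| Procedures, roll-out paragraph | Education, training, technical support; order of training | ED | Randomised order |
| Procedures, UH3 paragraph, first sentence | Engagement of providers | Site | Randomised order |
| Procedures, UH3 paragraph, next two sentences | Audit and feedback reports | Health system, all ED staff | Whole project, weekly |
| Procedures, baseline paragraph | Control time | Site | Up to the month before implementation |

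Only the fourth row gives the reports a timing of their own, and it does not mention crossover. Nor does its use of study period imply time after crossover. D) Recruitment and Informed Consent uses the same term for the visits that form the patient cohort, and that cohort has to include control-period visits.

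**Unit.** There are 35 EDs in 18 health systems: 35/18 = 1.94 per system, so at least one system has more than one ED. The site list in section 3 shows four under the lead institution. ED-level randomisation does not guarantee that sister EDs cross over together. Even if reports began only when a system's first ED crossed over, a system-wide rule could reach the others early.

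**Size.** The plan has no figure to reproduce: it states no effect size, baseline rate, intracluster correlation, power or step length. What follows is illustration under assumptions.

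Let f be the share of the full effect due to audit and feedback. Assume effects add on the model scale and reports work as well alone as within the package. Let c be the share of control time with reports running. With simple averaging of control time, the effect that remains is 1 − c·f, so the loss is at most f.

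| Assumed f | Least effect remaining, 1 − f | Most extra information needed, 1/(1 − f)² |
|---|---|---|
| 0.10 | 0.90 | 1.23× |
| 0.25 | 0.75 | 1.78× |
| 0.40 | 0.60 | 2.78× |
| 0.50 | 0.50 | 4.00× |

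On this averaging, c is below 1. Claims reach back 24 months before study initiation and the roll-in takes 12, which leaves 24 − 12 = 12 months of counted baseline before any report, if the roll-in opens the look-back. For an ED crossing over m months after initiation, with even patient flow and ignoring the one-month gap, c is at most m/(12 + m). Assumed m of 6, 12 and 24 gives 0.33, 0.50 and 0.67. With f = 0.25 the remaining effect is then 0.92, 0.88 and 0.83.

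The ceiling can still be reached. Suppose reports began at every ED at once and the model had a free effect for each calendar period. With full effect δ and crossover indicator X, the mean shift after that date is fδ + (1 − f)δX. The first term is common to all EDs and is absorbed by the period effects, so the estimate is (1 − f)δ despite the clean baseline. In both cases the ceiling is f. A patchier pattern of early reports could be worked out only from the actual dates.

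**The case against.** A reader might infer that the plan deliberately sends reports to control EDs, so that the comparator is usual care plus feedback and the trial estimates only the other three components. The documents do not support that, for these reasons:

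- The overview places the whole package, audit and feedback included, under the stepped wedge. The natural default is that component four starts with the rest.
- The sentence just before the disputed one follows the random order of implementation.
- The reports are meant to sustain participation in the initiative and to reinforce its pathways. Both presuppose that the ED has started.
- Taken to the letter, the wording proves too much. The project includes the UG3 phase, so all EDs would receive reports while the intervention was still being tailored and piloted.

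These points stand, and they may well describe what the sponsor intended. It also stands that f is unknown, that reports may do less without the training and decision support, and that some baseline is clean.

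They do not settle the text. The sequencing sentence governs engagement of providers; the next one changes the unit to the health system and the period to the whole project. A site could comply with it and still send reports in its control period. The mismatch between system and ED also survives the charitable reading.

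**Conclusion.** The concern holds as an inconsistency about when a core component starts, and by what unit. The overview, the roll-out paragraph and the baseline paragraph point to each ED's own implementation; the UH3 reporting sentences do not. Whether any control ED received, or was meant to receive, reports cannot be told from the documents.

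If some did, the likely direction is dilution toward no effect. The loss is at most f under the additive model above. For assumed f of 0.10 to 0.50 that is a loss of at most 10% to 50% of the effect, and nothing if no report preceded crossover. These values of f are assumptions, so (1 − f) should not be read as the expected result.

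**What to change.** **Wording.** Replace the UH3 reporting rule with: Audit and feedback reports start at each ED on its own randomised implementation date and continue weekly from then. No report goes to an ED, or to its staff in that role, during its control period, even if another ED in the same health system has crossed over.

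**Record.** Log the first-report date for each ED. E) Data Analysis, part b, says site-level variables were already assessed at implementation, so roll-out may have begun. In that case recover the dates from records; this is then the most useful part of the fix.

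**Analysis.** If any ED received reports before crossover, prespecify, before outcomes are analysed, a sensitivity analysis of the primary outcome that treats visits between first report and crossover as a separate exposure state or excludes them.

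**Cost.** The wording and log cost one or two sentences and one date per ED. Later EDs receive reports later, as the design already implies. The sensitivity analysis costs more: exclusion removes concurrent control time, lowers precision and leans harder on the calendar-time adjustment. In the extreme where reports began everywhere at once, exclusion leaves a before-after comparison, and a reports-only state cannot be told apart from calendar time. It should therefore stay a sensitivity analysis.

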We will recruit our participants for the provider interviews through a combination of word-of-mouth and email invitation through the healthcare systems points of contact established via the PRIM-ER study. After a participant expresses interest in participation, they will be contacted by [name] for Contextual Assessment or Senior Research Project Manager ([name]) or Co-Investigator [name] for CDS interview for an expanded explanation of the study, study procedures, their role as a participant, and potential risks and benefits. It will be clearly disclosed that the interview will occur via ZOOM teleconferencing and be recorded. Once the participant is read all study materials and information and had a chance to have all their questions answered, the recording device will be started, and the provider will be asked to provide verbal consent for participation. All qualitative interviews for this project, will follow the same protocol as outlined here.

E) Data Analysis

a. Dependent variables

ED disposition will be measured on the index ED visit, and will be a dichotomous variable for an acute care admission (Yes/No). Acute care admission will be defined as admission to a non-palliative service, and non-acute care admission will include admission to a palliative care service or unit, discharge to home, observation (without a change to inpatient status), or transfer to inpatient or outpatient hospice.

Healthcare utilization will be measured as ED revisits (count), inpatient days (count), home health use (Yes/No), and hospice use (Yes/No) in the 6 months from the index ED visit. These will be identified through revenue codes in each site's administrative data. We developed these measures of healthcare utilization based on the *Dartmouth Atlas Decedent Cohort Care Intensity Measures* to monitor the quality of end-of-life care in Medicare patients with serious chronic illness. ²⁸⁻³⁰

Survival will be measured in days from the index ED visit to death or 6 months, whichever is sooner.

b. Independent variables

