Table 1 outlines the independent variables. Independent variables were previously assessed at the time of site implementation. Healthcare system- and provider-level variables were collected by the project manager and via a provider survey at the level of each participating ED. Patient-level variables will be assessed using the CMS Research Data Assistance Center Master Beneficiary Summary File, Base (A/B/D) Segment. The Project Manager will also document if trainings occurred via in-person or virtually to understand more deeply the implementation of the QI initiative at each site.

Table 1. Independent Variables			
Variable	Coding	Source	
Implementation Period	Weeks from Time 0	Project Manager	
Healthcare system/ED-level variables			
Health System	Allegheny, Bay State, Beaumont, Brigham and Women's, Christiana Care, Henry Ford, [name] Anderson, NYU Langone, Ohio State University, Ochsner, Rutgers, Sinai, UC San Francisco, University of Florida, University of Pennsylvania, University of Utah, Yale New Haven	Project Manager	
ED	1—35	Project Manager	
ED Volume	30,000—49,999 visits, 50,000—69,999 visits, 70,000—89,999 visits, ≥ 90,000 visits	Project Manager	
Ownership	Nonprofit, Government, For Profit	Project Manager	
Emergency medicine residency training site	Yes/No	Project Manager	
Free-standing ED	Yes/No	Project Manager	
Dedicated ED social worker/care manager	Yes/No	Project Manager	
US Region	Northeast, Midwest, Southeast, Southwest, West	Project Manager	
Metropolitan Status+	Yes/No	Project Manager	
Outpatient palliative care	Yes/No	Project Manager	
EHR	Epic, Cerner	Project Manager	
Trauma center	Yes/No	Project Manager	
Patient variables			

Age	Years	Master Beneficiary Summary File, Base Segment
Gender	Female, Male, Other	Master Beneficiary Summary File, Base Segment
Race/Ethnicity	Asian, Black, Hispanic, White, North American Native, Unknown, Other	Master Beneficiary Summary File, Base Segment
Gagne index ²⁴	Count of conditions	Inpatient and outpatient RIF
+Population estimates by MSA are based on estimates of the civilian non-institutionalized population of the US as of July 1, 2013, from the 2013 National Health Interview Survey, National Center for Health Statistics, compiled according to the 2013 Office of Management and Budget definitions of core-based statistical areas. See http://www.census.gov/population/metro/ for more about metropolitan statistical area definitions.		

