Prior to conducting the outcome analyses, we will compare patients in each ED cluster with respect to patient, provider, and facility characteristics. We will assess whether any adjustments will need to be made in the final statistical models based on whether the differences are clinically meaningful. To account for nesting in the data structure (patients nested in hospitals), we will use mixed effect multi-level models to estimate effect sizes. We anticipate two sources of variation.

The **primary outcome** is the proportion of eligible patients whose disposition is to an acute care setting (inpatient, non-palliative service). The **secondary outcomes** include healthcare service utilization in the 6 months following the ED visit and survival times following the ED visit. The health utilization outcomes include receipt of ED revisits (count), home health services (yes/no), inpatient days (count), admission to an ICU

(yes/no), and admission to hospice (yes/no). The analysis of the effect of PRIM-ER on ED disposition in the context of a stepped-wedge design will be based on a Generalized Linear Mixed Model (GLMM). In particular, to assess the intervention effect, we will use a generalized linear binomial model with random site level effects. The analysis of site, provider, and patient-level characteristics that are associated with variation in impact of PRIM-ER will be based on extending the models used in the analysis plan for ED disposition, healthcare utilization in 6 months following the ED visit, and survival times to include independent variables related to the characteristics of interest.

5. Risks to Subjects

Any information collected from Emergency Department providers will be utilized solely for QI purposes and not analyzed for research.

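### Prior ED visits, inpatient days and ICU use can be derived from the look-back claims, but are not prespecified covariates for the matching 6-month outcomes, so precision is given up

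*Combined protocol and SAP*

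**What the plan says.** **Look-back.** The account of the research component, before part B (Inclusion and Exclusion Criteria), states: "We will then examine all inpatient, ambulatory, and carrier claims for the 12 months prior to each older adult's index ED visit". The purpose given is the Gagne Index, of which the same paragraph says: "It calculates a score based on the presence or absence of ICD-9s from inpatient and ambulatory claims in the prior year". It also gives the revenue codes that identify an ED claim.

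**Outcomes.** Part E, Dependent variables: "Healthcare utilization will be measured as ED revisits (count), inpatient days (count), home health use (Yes/No), and hospice use (Yes/No) in the 6 months". Part E, Methods: "The health utilization outcomes include receipt of ED revisits (count), home health services (yes/no), inpatient days (count), admission to an ICU", followed by hospice. ICU admission is in the second list only.

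**Covariates.** Part E, Independent variables: "Patient-level variables will be assessed using the CMS Research Data Assistance Center Master Beneficiary Summary File, Base (A/B/D) Segment". The patient rows of Table 1 are age, gender, race/ethnicity and the Gagne index, the last sourced from "Inpatient and outpatient RIF". Table 1 also has a calendar-time row, "Weeks from Time 0".

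**Adjustment rule.** Part E, Methods, says patients will be compared across ED clusters, and that adjustment will depend on whether the differences matter clinically. A binomial mixed model with random site effects is named for ED disposition. No model family or fixed covariate set is written for the utilization outcomes.

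**The concern.** A patient's past use of a service would be expected to predict later use of the same service. Here it is measured before the index visit, for everyone, in claims the study already examines.

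The Gagne index is only a partial substitute. It is a diagnosis-based mortality score that does not count visits, days or ICU stays, and the entry rule (score above 6) narrows its range.

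The planned balance check does not fill the gap either. It compares ED clusters with each other, and random site effects already absorb stable differences between EDs. The effect in a stepped wedge comes largely from before-after comparison within an ED, so unexplained patient-level variance carries much of the standard error.

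At stake is the precision of the effect on ED revisits, inpatient days and ICU admission, and a covariate choice left open until the data have been seen.

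**Working it through.** **1. Is the covariate absent?** The look-back yields one score. Table 1 has four patient variables, none of them prior use. No section adjusts a utilization outcome for its own earlier value. The omission stands.

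**2. Is there a stated figure to reproduce?** No. The plan gives an expected count of over 57,000 patients and 33 randomized EDs, but no alpha, power, effect size, ICC or number of steps. What follows is illustrative.

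**3. Precision.** Inputs from the plan: 33 EDs and 57,000 patients. Assumed: patients spread evenly; 33 steps of one ED (34 periods, m = 57,000/(33 × 34) = 50.8 per ED-period) or 11 steps of three (12 periods, m = 57,000/(33 × 12) = 143.9); total variance 1; fixed period effects. With ICC ρ, cluster autocorrelation c and partial correlation r beyond the Table 1 covariates, the covariance of one ED's period means is

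V = ρc·J + [ρ(1 − c) + (1 − ρ)(1 − r²)/m]·I

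where J is the all-ones matrix and I the identity. The variance of the effect is the treatment element of (Σ Z′V⁻¹Z)⁻¹, where Z holds the period indicators and the treatment indicator. Power is Φ(2.802/√ratio − 1.960), where ratio is adjusted over unadjusted variance and 2.802 = 1.960 + 0.842 sets unadjusted power at 80% (two-sided 5%).

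Variance reduction, with power in brackets:

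| Steps | ICC | Autocorrelation | r = 0.3 | r = 0.4 | r = 0.5 |
|---|---|---|---|---|---|
| 33 | 0.02 | 1.0 | 8.8% (83.5%) | 15.7% (86.2%) | 24.5% (89.7%) |
| 33 | 0.05 | 1.0 | 8.9% (83.5%) | 15.9% (86.3%) | 24.8% (89.8%) |
| 33 | 0.02 | 0.8 | 7.2% (82.9%) | 12.8% (85.1%) | 20.1% (88.0%) |
| 33 | 0.05 | 0.8 | 5.8% (82.3%) | 10.2% (84.1%) | 16.0% (86.4%) |
| 11 | 0.02 | 0.8 | 5.4% (82.2%) | 9.7% (83.9%) | 15.2% (86.0%) |
| 11 | 0.05 | 0.8 | 3.5% (81.4%) | 6.2% (82.5%) | 9.7% (83.8%) |
| 11 | 0.05 | 0.7 | 2.6% (81.0%) | 4.7% (81.9%) | 7.4% (82.9%) |

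Hand check: at autocorrelation 1.0 the ratio is close to 1 − r², that is 0.91, 0.84 and 0.75. For a ratio of 0.755, 2.802/√0.755 − 1.960 = 1.265, so power is 89.7%. At autocorrelation 1.0 the number of steps hardly matters. Below 1.0, fewer steps and a larger ICC shrink the gain, because the covariate is taken to reduce patient-level variance only and leaves ED-period variation untouched. At r = 0.2 the gain is about 0.5 to 1.6 points.

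**4. Drift.** Take r = 0.3, with 57,000/35 patients per ED, ICC 0.01 or 0.05 and autocorrelation 0.7-1.0.

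- *Unrelated to the randomized order.* A linear ED-specific drift in prior use, with SD 0.1-0.2 over the study, adds mean-zero error of about 0.08-0.31 of one standard error.
- *Aligned with implementation, and not captured by time or Table 1 covariates.* The bias is r × shift. Shifts of 0.05-0.20 SD give 0.3 × 0.05 = 0.015 to 0.3 × 0.20 = 0.06 outcome SD. Against standard errors of 0.0145-0.0255, that is from under one (0.015/0.0255 = 0.6) to about four (0.06/0.0145 = 4.1). Nothing in the documents shows such a shift.

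**The case against.** **The list is not closed.** A reader might infer that prior use cannot enter the models. The documents do not support that. Table 1 is offered as an outline, the protocol brings in provider survey data that the table does not list, and Methods leaves adjustment open. The accurate statement is that prior use is not prespecified.

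**Drift is not shown to be bias.** A reader might infer that ED case-mix drift distorts the PRIM-ER effect. Order is randomized over 33 EDs, so drift unrelated to order is noise. Random site effects absorb stable ED differences, and the listed calendar-time variable can absorb common trends if it is put in the model. The 12-month roll-in is the plan's remedy for prevalence-incidence bias, not evidence of drift. This objection stands.

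**The gain may be small.** With 11 steps, ICC 0.05 and autocorrelation 0.8, no tested correlation gains 5 points. The 80% start also matters: at unadjusted standard errors of about 0.014-0.025 SD it implies a true effect of only about 0.04-0.07 SD. At 0.1 SD, power is already about 98% or more. From a 95% start, the largest gain at r = 0.5 is 3.6 points. This also stands, and is why the size is given as a range.

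**ICU admission is binary.** In a logistic model, adjustment changes the conditional odds ratio and need not shrink its standard error. The figures therefore do not carry over directly to ICU admission.

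**Prior use may be post-intervention.** For an index visit more than 12 months after an ED's crossover, the whole look-back falls after PRIM-ER began there. A difference between models with and without the term could then mean drift removed or effect adjusted away. The hazard is real but limited: patients enter at their first qualifying visit, so earlier visits to an implemented ED were mostly made before they met the score threshold.

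**A more basic gap exists.** No model family or covariate set is written for these outcomes. That is true, and the fix below should be made as part of filling it.

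**Conclusion.** The point holds as an efficiency and prespecification issue for three secondary outcomes. Baseline values available from claims the study already examines are not planned covariates, and the adjustment rule is data-driven. Under the assumed ICC (0.02-0.05), autocorrelation (0.7-1.0), 11 to 33 steps and partial correlation (0.3-0.5), the variance of the effect on the count outcomes could fall by about 3-25%, or about 1 to 10 points of power from an assumed 80%. A lower correlation or a higher starting power makes the gain smaller.

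The linear variance formula is an approximation even for counts. The documents support neither a claim of bias nor any effect of this omission on the primary outcome. The change is worth making because it costs little and removes a post hoc choice; the trial's validity does not depend on it.

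**What to change.** 1. Add three patient variables to Table 1: number of ED visits, number of inpatient days, and any ICU stay, each in the 12 months before the index visit and excluding that visit.
2. Prespecify each in its matching 6-month model: prior ED visits for ED revisits, prior inpatient days for inpatient days (for example log(1 + count) or a spline), prior ICU stay for ICU admission. Include the Table 1 patient covariates and calendar time in the same models, whatever the observed imbalance.
3. Take baseline and outcome from the same Medicare claims. Dependent variables refers to each site's administrative data, while the research component uses Medicare claims. Reconcile these, and the two outcome lists on ICU admission.
4. Report each model without the prior-use term. Also report a version that either keeps prior use only where the look-back precedes that ED's implementation date, or excludes look-back use at participating EDs that had already implemented. The first loses late patients' look-back and the second measures prior use differently over time, so both are sensitivity analyses only.
5. Tabulate prior use by ED, before and after implementation.

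Cost: SAP wording and a few lines of code on claims the study already examines, with no new patients or data. The downside is the possible post-crossover look-back, which step 4 makes visible.
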